ISPOR	International Society for Pharmacoeconomics and Outcomes Research
OPCRD	Optimum Patient Care Research Database
SD	Standard Deviation
SES	Socio-Economic Status
SNOMED CT	Systemized Nomenclature of Medicine – Clinical Terms
UK	United Kingdom

3. Introduction

3.1 Background

Vitiligo is an acquired, non-contagious skin disorder characterised by depigmented patches of skin that may appear in a localised or very generalised distribution, and affecting 0.5-2.0% of the global population.(1) The exact cause of the loss of functioning melanocytes in vitiligo remains unknown, but is likely to be resulted from the complex interplay of genetics, oxidative stress, and autoimmunity.(2)

Although vitiligo is typically asymptomatic, recent Pfizer-funded research has demonstrated the condition substantially affects psychological wellbeing.(3) This previous study showed that people with vitiligo have a considerable excess mental health burden when compared with people without vitiligo. It also showed that, in people with vitiligo, mental health comorbidity is associated with higher levels of healthcare utilisation, time off work, and unemployment.(3) This increased burden could be due to the unpredictable prognosis, the current lack of cure, the perception and emotional burden associated with the visibility of vitiligo, or a combination of these factors.

There is substantial scope to extend the initial analysis, with a comprehensive assessment of sociodemographic disparities in healthcare utilisation and in the burden of mental health comorbidity in people with vitiligo. Whilst the previous Pfizer-funded study demonstrated a difference by ethnicity in the mental health impacts of vitiligo (with vitiligo associated with a greater mental health burden in people of non-white ethnicity), the study was not designed to assess this as a primary outcome. Further analysis is required to fully understand these potential relationships as well as provide critical information on whether there is a socio-economic (SES) gradient in the mental health impacts of vitiligo. The previous study did not assess other potential disparities in management, such as healthcare utilisation of primary care encounters or dermatology services.

There is also substantial scope to expand on the previous study to provide, for the first time, a greater understanding of the total burden of vitiligo across the population, including reporting lifetime risk estimates for vitiligo, across sociodemographic groups. It is likely that substantial disease burden differences exist across these groups.

A comprehensive assessment of potential disparities in healthcare utilisation in vitiligo, mental health and social impact, and lifetime risk are needed. This research would both strongly complement previous Pfizer-funded work and support the use of newer therapies in vitiligo.

3.2 Purpose of Analysis

This study will provide the first estimate of the cumulative lifetime risk of vitiligo in the population overall, and by important sociodemographic groups, including age, sex, ethnicity and SES, which will provide key data to show the relative burden of vitiligo across the aforementioned groups. These approaches allow creation of cumulative lifetime risk plots which provide an excellent and accessible way to display the relative disease burden across groups.

This study will provide a detailed assessment of any sociodemographic disparities in comorbidities and social impact that occurs in people with vitiligo. This will include any differences in mental health impact of vitiligo by sociodemographic. It will also include a description of any sociodemographic disparities in time off work (“sick leave”) or unemployment in people with vitiligo.

This study will also provide a detailed assessment of any sociodemographic disparities in healthcare utilisation in people with vitiligo with comparison across sociodemographic. This will include analysis of utilisation of primary care services, mental health referrals as well as referrals to secondary care (dermatology).

4. Study objectives and endpoints

4.1 Study Objectives

The overall purpose of the study is to provide an estimate of the lifetime risk of vitiligo in the population overall and by important sociodemographic groups. Moreover, to do a subgroup analysis in the vitiligo population to identify health-related disparities across people in different sex, age, deprivation and ethnicity.

4.2 Primary Objectives

4.2.1 Objective 1

Describe the total burden of vitiligo (cumulative lifetime risk) across sociodemographic subgroups.

4.3 Secondary Objectives

4.3.1 Objective 2

Describe any disparities in the burden of mental health outcomes, including depression and anxiety in people with vitiligo across sociodemographic subgroups.

4.3.2 Objective 3

Describe any disparities in the association of vitiligo with parasuicide/suicide attempts, adjustment disorder and sleep disturbances associated with vitiligo across sociodemographic subgroups.

4.3.3 Objective 4

Describe any disparities in vitiligo-associated healthcare utilisation across sociodemographic subgroups.

4.3.4 Objective 5

Describe any disparities in vitiligo-associated work impact (time off work for illness and unemployment) across sociodemographic subgroups.

4.4 Primary Endpoints

Objective	Endpoints
1	An incident diagnosis of vitiligo is the date of the first diagnosis code in the record and no alternative diagnosis that merits exclusion (other causes of skin hypopigmentation) diagnosed within a one-year period (six months before or after their first vitiligo diagnosis code).

Table 1: Primary endpoints.

4.5 Secondary Endpoints

Objective	Endpoints
2	Mental health condition outcomes will be assessed up to two years post-vitiligo diagnosis, including history of prior mental health condition and will comprise of depression (record of any depressive episodes and/or major recurrent depression diagnosis) and anxiety disorders, defined by the International Statistical Classification of Diseases and Related Health Problems 10th Revision (ICD10) classification, and identified using algorithms validated for use in UK primary care data (See previously published codes lists: (4))
3	Other mental health condition outcomes will be assessed up to two years post-vitiligo diagnosis and will comprise of parasuicide/suicide attempts, adjustment disorder and sleep disturbance, defined by the International Statistical Classification of Diseases and Related Health Problems 10th Revision (ICD10) classification, and identified using algorithms validated for use in UK primary care data (See previously published codes lists: (4))

4	Healthcare utilisation outcomes will comprise primary care visits, dermatology referrals, mental health referrals (including but not limited to those via IAPT; Improving Access to Psychological Therapies and psychiatric reviews) in the two years post-vitiligo diagnosis.
5	Unemployment in the two years post-vitiligo diagnosis will be identified using Read codes relating to unemployment recorded in the primary care record or the issuing of IB113 or ESA113 forms (See previously published codes lists: (4)). Time off work in the two years post-vitiligo diagnosis will be indicated by the issuing of Med 3 certification from primary care (Statement of Fitness for Work certification) (See previously published codes lists: (4)).

Table 2: Secondary endpoints.

5. General Study Design and Plan

The study will use retrospectively collected anonymised data from all eligible people contributing to the Optimum Patient Care Research Database (OPCRD)(5) at the date of data extraction. A matched-cohort design will be used for incident (and prevalent) vitiligo related healthcare utilisation, mental health conditions and work impacts. Lifetime risk will be calculated using adapted survival analysis to account for the competing risk of death and will be estimated for the population overall and separately in sociodemographic subgroups of interest.

All adults and adolescents (aged 13+ for disparity objectives 2-5 inclusive) contributing to OPCRd during the study period (January 1, 2004 and December 31, 2020 inclusive). People who have opted out of record data sharing will not be included (approximately 1.8% of the adult population) and have not been uploaded to the OPCRd database.

Cumulative lifetime risk of vitiligo will be estimated (using the method described in the statistical methods below) using cases of incident vitiligo occurring during the observational study period (January 1, 2004 and December 31, 2020 inclusive). A matched-cohort design will be used for incident (and prevalent) vitiligo related mental health conditions, healthcare utilisation and work impacts. For all analyses, the overall result including both adults (aged 18+) and children (aged 13-17) will be published, with stratification by age, sex, deprivation and ethnicity.

5.1 Study design

This is a non-interventional study.

5.2 Total disease burden; cumulative lifetime risk

A cross sectional design (incidence) will be used to assess the total disease burden of vitiligo, stratified by sociodemographic groups.

5.3 Disparities in the impact of vitiligo on mental health, healthcare utilisation and work impact

A matched-cohort design will be used for incident (and prevalent) vitiligo related: Mental health conditions; work impact; healthcare utilisation.

5.4 Data Source and Read codes

The OPCR(5) is a well-established primary care network in the UK. The database contains complete data on all events and clinical entities coded in UK primary care. These include sociodemographic factors and demographic information, clinical diagnoses, laboratory test results, primary care issued prescriptions, process of care codes (e.g. specialist dermatology reviews), and anthropometric measurements (e.g. BMI), and are coded using the Read coding and Systemized Nomenclature of Medicine – Clinical Terms (SNOMED CT) coding systems.(6)

5.5 Data Governance

This study is based wholly on data from the OPCR (www.opcrd.co.uk) obtained under a limited license from Optimum Patient Care Limited and its execution is approved by recognised experts affiliated to the Respiratory Effectiveness Group.

Data from the OPCR are available under license for clinical research which is subject to relevant approvals. For additional information visit: www.opcrd.co.uk.

5.6 Data Extraction

Individual patient data was anonymised at the point of data extraction. All data will remain in anonymised form and will be held on a secure server operated by Momentum Data. The data will not be used for any purposes other than for the research which is described in the respective protocols and which has been approved by the OPCR ADEPT Committee.

5.7 General Study Population

5.7.1 Vitiligo Definition

People diagnosed with vitiligo will be identified using diagnostic Read and SNOMED CT codes which are specific to vitiligo. (Appendix 1) A diagnostic algorithm will be used to facilitate robust case identification, identifying anyone with a specific diagnosis code followed by exclusion of anyone with a diagnosis code for an alternative depigmenting

disorder coded within a one-year period (six months before or after their first diagnosis code). The list of alternative depigmenting disorders is shown in Appendix 2.

Incident cases will be defined as people with a first ever diagnosis code of vitiligo during the study period. People with a diagnosis of vitiligo prior to the study period will be excluded. Each case will be assigned an index date at the time of their vitiligo diagnosis.

5.7.2 Sociodemographic subgroups

Age, sex, deprivation and ethnicity will comprise the sociodemographic factors used for stratification of the outcome measures.

Age will be stratified into four age categories: 13-17 (adolescents), 18-20, 30-49, 50+.

Ethnicity will be grouped using the standardised definitions of major UK ethnic groups: White, Black, Asian, mixed, and others. (7)

Deprivation will be defined using the national deprivation measure; index of multiple deprivation (IMD) and stratified into quintiles of deprivation according to the national distribution. (8) IMD is calculated at the point of data extraction, using patient postcode (practice postcode where patient postcode is not available).

6. Sample Size Calculations

A sample size calculation is only applicable to the incidence of mental health conditions of anxiety and depression in people diagnosed with vitiligo.

Assuming 80% power, a 5% level of statistical significance and a background population prevalence of 15% for anxiety and 10% for depression,(9), our anticipated sample size for vitiligo (n = 8,000) will be sufficient to detect a risk difference of 1.11% in anxiety between those with and without vitiligo, and 1.12% difference in depression between those with and without vitiligo. Sample size calculations were performed in OpenEpi,(10) results are presented using methods of Kelsey.(11)

7. Populations to be Analysed

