7.1 Inclusion Criteria

People must meet all the following inclusion criteria to be eligible for inclusion in the study:

- The cohort for the endpoint analysis will consist of all adults and adolescents (aged 13+) contributing to OPCR during the study period.

- The cohort for the lifetime risk analysis will consist of all people contributing to OPCRCD during the study period.
- The vitiligo cohort consists of people newly diagnosed with vitiligo at any point during the study period.

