7.2 Exclusion Criteria

People meeting any of the following criteria will not be included in the study:

- People with the alternative non-vitiligo diagnoses (other hypopigmenting conditions).
- People with vitiligo diagnosis within 6 months of practice registration.
- People without vitiligo with less than 1 year of follow up within the dataset.
- People over the age of 95 (for those reaching age 95 during the follow up period, follow up was censored at age 95).

People who have opted out of record sharing are not included (approximately 1.8% of the adult population).

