Only cases and matched controls aged 18-65 will be considered for this analysis. Work impact outcomes (unemployment and time off work for illness) will be defined by the first occurrence of a relevant code in primary care record up to two years post index date. Cox proportional hazards regression will be used to estimate the excess risk of these outcomes in vitiligo cases versus matched controls. Results will be described as hazard ratios.

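### The four age bands leave out ages 21 to 29, so these people appear in no age-stratified result for objectives 2-5

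*Combined protocol and SAP*

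**What the plan says.** Section 5.7.2 names the subgroup factors: "Age, sex, deprivation and ethnicity will comprise the sociodemographic factors used for stratification of the outcome measures". It then sets the bands: "Age will be stratified into four age categories: 13-17 (adolescents), 18-20, 30-49, 50", the last band being open-ended. No other section defines age strata.

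The populations have no matching gap:

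- Section 7.1, for the endpoint analyses: "The cohort for the endpoint analysis will consist of all adults and adolescents (aged 13+) contributing to OPCR during the study period".
- Section 7.2 sets the only general upper limit: "People over the age of 95 (for those reaching age 95 during the follow up period, follow up was censored at age 95".
- Section 8.3 narrows objective 5: "Only cases and matched controls aged 18-65 will be considered for this analysis".

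On reporting, section 5 says that results for adults and for those aged 13-17 "will be published, with stratification by age, sex, deprivation and ethnicity", and it applies this to all analyses.

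**The concern.** Objectives 2-5 exist to describe disparities across sociodemographic subgroups, and age is one of the four factors that define those subgroups. A set of bands for that purpose should place every eligible person in exactly one band. These bands go from 18-20 directly to 30-49.

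Three things follow if the definition is applied literally:

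1. Cases aged 21-29 and their age-matched controls enter the overall estimate but no age stratum, so the age-specific counts do not add up to the total.
2. The only stratum between adolescence and age 30 covers three years of age. A reader could take it for the young-adult result, when it describes people aged 18-20 only.
3. If an analyst notices the gap and repairs it after seeing the data, the bands on a main reporting dimension will have been chosen after the fact, with no record of what was planned.

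**Working it through.** There is no plan figure to reproduce, because the plan gives no count by age. The check is one of coverage, followed by an illustration of size.

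**Inputs**

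- Bands: 13-17, 18-20, 30-49, 50+ (section 5.7.2).
- Eligible ages for objectives 2-5: 13 and over (section 7.1), up to 95 (section 7.2).
- Eligible ages for objective 5: 18-65 (section 8.3).
- Anticipated cases: 8,000 (section 6). Controls: up to four per case (section 7.3).

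**Coverage, ages 13 to 95**

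- Eligible single years: 95 − 13 + 1 = 83.
- Years inside a band: 5 (13-17) + 3 (18-20) + 20 (30-49) + 46 (50-95) = 74.
- Years in no band: 83 − 74 = 9, namely 21, 22, 23, 24, 25, 26, 27, 28 and 29.
- Years in two bands: none.

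**Coverage, objective 5**

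- Eligible single years: 65 − 18 + 1 = 48.
- Years in no band: 9, and 9/48 = 18.8% of the age range. This is a share of ages, not of patients.

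**Illustration of size (assumptions needed)**

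- Ages 18-29 span 12 single years, of which 9/12 = 75% have no band. That is 75% of young adults only if age is evenly spread over 18-29.
- If people aged 21-29 make up 8-15% of cases (assumed; the documents give no share), the unassigned cases number 0.08 × 8,000 = 640 to 0.15 × 8,000 = 1,200.
- With the maximum of four controls each, the unassigned controls number 4 × 640 = 2,560 to 4 × 1,200 = 4,800.
- If age is evenly spread and event rates are similar across 18-29, an interval based on 18-20 is wider than one based on 18-29 by a factor of √(12/3) = 2.

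**Check of the repair**

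With the second band read as 18-29, the count is 5 + 12 + 20 + 46 = 83, so every age from 13 to 95 falls in exactly one of four bands. A separate 21-29 band would also close the gap, but it would make five bands against the stated four.

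**The case against.** The strongest reply is that this is a one-digit slip, or a misreading when the PDF was converted to text, and not a decision to omit anyone. The plan announces four categories, the other boundaries (17/18 and 49/50) join cleanly, and no criterion excludes ages 21-29. Tabulating the strata against the total would expose the gap at once. That account of the cause is probably right. It does not remove the point: the error stands in the operational definition, no other section corrects it, and the repair has to be inferred. If the source document prints 18-29, the point falls away, but nothing in the text shows that it does.

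The reply is also right on scope. The primary objective is untouched, since section 8.2 lists lifetime risk by sex, ethnicity and SES and plots it against age without these bands. People aged 21-29 stay in the overall results, in the sex, ethnicity and deprivation strata, and in the matching. The sample-size statement in section 6 does not use age bands.

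Finally, the patient counts and the interval width rest on assumptions and not on the documents. That stands too, and those figures should be read only as an indication of scale.

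**Conclusion.** The concern holds. As written, nine single years of age, 21 to 29, are eligible for objectives 2-5 but belong to no age stratum. This follows from the text and needs no assumption. The consequence is confined to age-stratified results: strata that do not sum to the total, and a young-adult result drawn from ages 18-20 alone.

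The number of people affected cannot be derived from the documents. The range of 640-1,200 cases depends wholly on the assumed 8-15% share. The doubling of interval width depends on an even age spread and similar event rates within 18-29. The overall comparisons remain valid, so this is a correction that should be made before analysis and not a flaw that undermines the study.

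**What to change.** Check the source document and confirm the intended bands. If the second band was meant to be 18-29, correct section 5.7.2 so that the bands are 13-17, 18-29, 30-49 and 50+. This keeps the stated four categories and covers the whole cohort without gaps.

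Add one sentence saying that age for stratification is age at the index date. Section 7.3 already matches at that date, but section 5.7.2 does not say which age defines the stratum.

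The cost is one figure and one sentence. No change to data, matching or models is needed if the correction is recorded before the stratified analyses are run.

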7.3 Matching Process

For objectives 2-5, controls for each vitiligo case will be identified from the pool of people without a vitiligo diagnosis registered in the OPCRCD database at the time of vitiligo diagnosis for the case. Vitiligo cases will be eligible as controls up until the date of their vitiligo diagnosis (at which date their follow-up will be censored if selected as a control).

Each case will be assigned an index date at the time of their vitiligo diagnosis. Corresponding controls assigned to each case will have the same index date.

Each individual with vitiligo will be matched at their index date with up to four unaffected controls. Controls cannot be diagnosed with vitiligo at the date of matching and will require at least one year of follow-up time to minimise the risk of a non-recorded existing diagnosis of vitiligo. Time-updated exact matching will be performed by age, sex, ethnicity and deprivation, selected from the pool of eligible people registered in the same GP practice.

If required, a combination of time-dependent propensity score matching and exact matching will be performed to create a baseline matched dataset.

The matching process is subject to change depending on the feasibility of the mentioned matching process during the initial exploration of the data. The produced baseline matched dataset will be used for all analyses for objective 2-5.

8. Statistical Analysis

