8.1 Statistical Principles

Mean, standard deviation (sd) and any other statistical measures, will be reported to one decimal place. Continuous data will be summarised in the form of means, sd, median, interquartile range (IQR) and range as appropriate. Categorical data will be summarised using the frequencies and proportions. Chi-squared and t-tests will be performed to compare the frequency of dichotomous variables and the values of continuous variables where relevant. 95% CIs will be reported for main effect sizes. Statistical significance will be assessed using $p < 0.05$. Actual p-values will be reported except for p-values less than 3 decimal places which will be reported as “ < 0.001 ”. P-values > 0.1 will be reported to one decimal place, p-values between 0.01 and 0.1 will be reported to 2 decimal places, and p-values between 0.001 and 0.01 will be reported to three decimal places.

The assessment of any associations with baseline characteristics and the outcomes of interest (objectives 2-5) will be assessed using logistic regression (prevalent and incident outcomes), Cox proportional hazards (time to event outcomes) and Poisson regression (repeated event outcomes) models. Three different adjustment sets will be used for each endpoint analysis. These include: an unadjusted model, a sex and age adjusted model, and a multivariable model with an adjustment set of: age, sex, BMI, smoking status, alcohol use, and common comorbidities: type 2 diabetes, hypertension, atrial fibrillation, angina, acute myocardial infarction, stroke, heart failure, chronic liver disease, dementia, rheumatoid arthritis, asthma, chronic obstructive pulmonary disease, chronic kidney disease stages 3-5, malignancy and inflammatory bowel disease.

Assumptions of statistical approaches will be assessed, and transformations used if necessary.

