8.3 Secondary Endpoint Analysis

Objective 2

Anxiety and depression outcomes will be captured if occurring prior to, or within two years of, an individuals' study index date. Binary outcome logistic regression model outputs will be used to compare the burden of anxiety and depression in vitiligo cases compared to matched controls. Furthermore, additional analyses for new onset anxiety and depression outcomes will be conducted, excluding people with a previous record of the respective mental health condition. Anxiety and depression outcomes will be defined by the first occurrence of a relevant code in the primary care record up to two years post index-date. Cox proportional hazards regression will be used to estimate the excess risk of anxiety and depression outcomes in vitiligo cases versus controls. Results will be described as hazard ratios.

Objective 3

Parasuicide/suicide attempts will be defined by the first occurrence of a relevant code in the primary care record up to two years post index-date. People with a previous record of parasuicide/suicide attempt will be excluded from the calculations. Cox proportional hazards regression will be used to estimate the excess risk of parasuicide/suicide attempts in vitiligo cases versus matched controls. Results will be described as hazard ratios.

Adjustment disorder and sleep disturbance will be defined by the first occurrence of a relevant code in the primary care record up to two years post index-date. People with a previous record of the adjustment disorder will be excluded from the from the adjustment disorder endpoint analysis. Cox proportional hazards regression will be used to estimate the excess risk of the relevant condition in vitiligo cases versus matched controls. Results will be described as hazard ratios.

Objective 4

Dermatology referral and mental health referral or reviews will be defined by the first occurrence of a relevant code in the primary care record up to two years post index date. Cox proportional hazards regression will be used to estimate the excess risk of these outcomes in vitiligo cases versus matched controls.

For primary care encounters reviews, defined as a rate of encounters within two years after the index date, will be compared using generalised linear models with time-at-risk as an offset. Results will be described as incidence rate ratios.

Objective 5

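### The detectable differences of 1.11% (anxiety) and 1.12% (depression) in Section 6 cannot both be risk differences from one set of inputs; they may be odds ratios labelled as percentages

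*Combined protocol and SAP*

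**What the plan says.** Section 6 of the combined protocol and SAP confines its sample size calculation to anxiety and depression. It sets out the inputs as "Assuming 80% power, a 5% level of statistical significance" and a "background population prevalence of 15% for anxiety and 10% for depression". From these it concludes that the anticipated 8,000 people with vitiligo "will be sufficient to detect a risk difference of 1.11% in anxiety between those with and without vitiligo, and 1.12% difference in depression". It names OpenEpi as the software and Kelsey as the method.

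Section 6 gives neither the sidedness of the test nor the number of controls per case. Two other sections bear on these:

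- Section 7.3: each case is "matched at their index date with up to four unaffected controls".
- Section 8.1: "95% CIs will be reported for main effect sizes", with significance judged at p < 0.05.

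Section 8.3 gives the analysis of mental health burden (Objective 2): "Binary outcome logistic regression model outputs will be used to compare the burden of anxiety and depression in vitiligo cases" against matched controls. The natural effect measure of that model is an odds ratio.

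**The concern.** Binomial variance is larger at 15% than at 10%. With the same number of cases, level, power and control ratio, the smallest detectable absolute difference must therefore be clearly larger for anxiety than for depression. The plan prints nearly equal values, with depression slightly the larger. So at least one figure is wrong, or the two are not risk differences.

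This is the plan's only power statement. Taken at face value, it makes the study look more sensitive for anxiety than it is (two-sided, at up to four controls per case). If odds ratios were meant, the anxiety effect in absolute terms is larger again than the printed percentage suggests.

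**Working it through.** **Inputs.** From Section 6: 8,000 cases, 80% power (z = 0.842), 5% level, p0 = 0.15 for anxiety and 0.10 for depression. Assumed, because Section 6 is silent: a two-sided test (z = 1.960), in line with the 95% intervals of Section 8.1, and r = 4 controls per case, the maximum in Section 7.3. One-sided tests (z = 1.645) and r = 1 to 3 were also tried.

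**Formula (Kelsey, unmatched).**

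n = (z_a + z_b)² × p̄(1 − p̄) × (r + 1) / (r d²), with p1 = p0 + d and p̄ = (p1 + r p0)/(1 + r).

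**Step 1: try to reproduce the printed pair.** Solving for d at n = 8,000 gives, in percentage points:

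| Test | Controls per case | Anxiety | Depression | Depression / anxiety |
|---|---|---|---|---|
| Plan as printed | not stated | 1.11 | 1.12 | 1.01 |
| Two-sided | 1 | 1.62 | 1.37 | 0.85 |
| Two-sided | 2 | 1.39 | 1.17 | 0.84 |
| Two-sided | 3 | 1.30 | 1.10 | 0.84 |
| Two-sided | 4 | 1.26 | 1.06 | 0.84 |
| One-sided | 1 | 1.43 | 1.21 | 0.85 |
| One-sided | 4 | 1.12 | 0.94 | 0.84 |

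No row gives the printed pair. The ratio hardly moves because n, z and r cancel, leaving approximately √(0.10 × 0.90 / (0.15 × 0.85)) = √(0.0900/0.1275) = 0.84.

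**Step 2: power at the printed differences, r = 4.** Power = Φ(d/SE − z_a), with SE = √(p̄(1 − p̄) × 1.25/8,000).

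- Anxiety, d = 0.0111: p̄ = (0.1611 + 4 × 0.15)/5 = 0.15222, SE = 0.004490, d/SE = 2.472. Two-sided: Φ(0.512) = 69.6%. One-sided: Φ(0.827) = 79.6%.
- Depression, d = 0.0112: p̄ = (0.1112 + 4 × 0.10)/5 = 0.10224, SE = 0.003787, d/SE = 2.957. Two-sided: Φ(0.997) = 84.1%. One-sided: Φ(1.313) = 90.5%.

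A formula with separate variances under the alternative gives 69.3% and 83.4% two-sided, so the choice of formula matters little. For 80% power, two-sided at r = 4, the printed anxiety difference needs about 10,280 cases and the printed depression difference 7,179.

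**Step 3: read the figures as odds ratios.** Put p1 = OR × p0 / (1 − p0 + OR × p0) into the same formula, two-sided, r = 4:

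| Outcome | Odds ratio | p1 | Risk difference (points) | Cases needed |
|---|---|---|---|---|
| Anxiety | 1.10 | 0.1626 | 1.26 | 8,037 |
| Anxiety | 1.11 | 0.1638 | 1.38 | 6,671 |
| Depression | 1.11 | 0.1098 | 0.98 | 9,369 |
| Depression | 1.12 | 0.1107 | 1.07 | 7,900 |

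The smallest two-decimal odds ratios that need no more than 8,000 cases are 1.11 and 1.12, the two printed numbers. No other Kelsey combination of control ratio (1 to 4), sidedness and scale (risk difference, risk ratio, odds ratio) gave this pair by the same rule.

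**The case against.** **The text claims sufficiency, not a minimum.** Section 6 says that 8,000 is enough to detect these differences. It does not say that each is the smallest difference detectable at exactly 80% power, so the ordering argument need not bind. For depression this stands: 1.12 points is attainable, with power to spare. For anxiety it fails. At 1:4, power for 1.11 points is about 70% two-sided and 79.6% one-sided, where 80% would need about 8,095 cases. Two-sided, even 100 controls per case would only bring the detectable difference down to 1.12 points.

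**The size of the anxiety shortfall rests on assumptions.** This stands. The 70% figure needs a two-sided test and a full four controls per case. One-sided at 1:4, the anxiety shortfall almost vanishes, but the two figures then have 79.6% and 90.5% power, so they still do not share one power.

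**The odds-ratio explanation is fragile.** This partly stands. Section 6 mentions no odds ratio. The exact detectable odds ratios are 1.1002 and 1.1192, which round conventionally to 1.10 and 1.12; the match requires rounding up to a value that 8,000 cases can support. Under the Fleiss formula, 1.12 for depression needs 8,029 cases and the match is lost. Kelsey is the cited method, however, and the inconsistency in the printed pair does not depend on this explanation.

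**Little depends on the calculation.** The study uses all eligible records, so the available data set the sample size. This stands, and it limits the consequence to a misleading statement of sensitivity.

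**Conclusion.** The paragraph is wrong as written. That the printed values cannot both be the detectable risk differences for one set of inputs needs no assumption about sidedness or control ratio. Assuming a two-sided test at 1:4, the detectable differences are about 1.26 and 1.06 points: the anxiety figure is understated by 0.15 points, and the depression figure is overstated by 0.06. Matching is up to four controls, so 1:4 is the best case for anxiety. All values come from an unmatched two-proportion formula, as in the cited method, and are approximate for the matched analyses.

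Mislabelled odds ratios are the likeliest source, but only the OpenEpi output can confirm it. The effect is confined to the power statement for secondary outcomes. It should be corrected, but it does not put the design in question.

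**What to change.** Check the OpenEpi output, then restate Section 6 with the effect measure, sidedness and control ratio. If risk differences are intended, the following would serve:

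> With 8,000 cases, four controls per case, 80% power and a two-sided 5% level, the detectable risk differences (Kelsey, unmatched approximation) are about 1.26 percentage points for anxiety (15% v 16.26%; odds ratio 1.10) and 1.06 for depression (10% v 11.06%; odds ratio 1.12).

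Because some cases may have fewer than four controls, it would help to add the other two-sided rows of the first table (1 to 3 controls). If odds ratios of 1.11 and 1.12 were intended, label them as such and print the equivalent risk differences, 1.38 and 1.07 points, beside them.

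The cost is one corrected paragraph. No extra patients are needed and no endpoint or model changes; read as a risk difference, the anxiety figure becomes slightly less favourable.
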